1.5.4 Micronised progesterone for administration (Utrogestran)

Details of micronised progesterone are contained in the current version of the SmPC. Of note, much of the information in the SmPC relates to the approved use of micronised progesterone in combination with oestrogen in post-menopausal women with an intact uterus at potential risk of endometrial cancer, as hormone replacement therapy.

Micronised progesterone is not taken with food in routine practice as this increases its bioavailability. The recommended daily dose is 100 mg or 200 mg daily at bedtime.

With regard to potential drug interactions, drugs known to induce hepatic CYP450-3A4 such as anti-epileptic agents (phenytoin, carbamazepine) may increase the metabolism and elimination of progesterone; ketokonazole and other inhibitors of CYP450-3A4 may increase the bioavailability of progesterone.

The incidence of adverse drug reactions with oral micronised progesterone was calculated as 1.43/1,000 patient years', corresponding to approximately 1.5 spontaneously reported cases in every 1000 patients exposed. Clinical trial data comparing micronised progesterone in combination with conjugated oestrogen to conjugated oestrogens alone or placebo suggest an excess of headache and breast tenderness in those taking micronised progesterone. Somnolence, fatigue or transient dizziness may occur 1 to 3 hours after intake of micronised progesterone and is reported to be associated with high doses of progesterone. Withdrawal vaginal bleeding may occur in women in the week following discontinuation.

Micronised progesterone is absorbed by the digestive tract and in healthy volunteers plasma progesterone levels were maximum 2.2 +/- 1.4 hours following administration. Progesterone is highly (96%-99%) protein bound, primarily to serum albumin and transcortin. Progesterone is metabolised primarily by the liver predominantly 20 α hydroxy- Δ 4 α - prenone and 5 α - dihydroprogesterone. The elimination half-life observed is 16.8 +/- 2.3 hours with urinary elimination accounting for 95% in the form of glycoconjugated metabolites. The pharmacokinetics of micronized progesterone are reported as independent of dose. Individual pharmacokinetic characteristics were maintained over several months.

2. AIMS AND ENDPOINTS

The overall objective is to provide (a) pharmacokinetic data to guide the dosing of micronised progesterone as a steroid-sparing agent for the treatment of brain tumour oedema, (b) evidence of feasibility and (c) preliminary evidence of efficacy to underpin a subsequent definitive randomised controlled trial comparing micronised progesterone and placebo. Prior to a definitive randomised controlled trial several key issues need to be addressed:

- The pharmacokinetics of intermediate-dose oral micronised progesterone require further characterisation,
- The ability to achieve the target steady state plasma progesterone levels requires confirmation as does tolerability in this patient population
- Finally, subsequent trials will greatly benefit from piloting the patient reported outcome measures (PROMs) of QoL, the structured dexamethasone reduction protocol and a preliminary assessment of the efficacy of micronised progesterone as a dexamethasone sparing agent

This information could not be obtained from pre-clinical studies. Whilst well-characterised brain tumour models do exist, our systematic review (2) has shown that no suitable pre-clinical model exists to study peri-tumoural oedema. Furthermore, patients often experience symptomatic

relief within hours of receiving dexamethasone before radiological improvement becomes apparent, which could not be adequately addressed in pre-clinical models. Finally, our approach respects the principles of the 3Rs (Replacement, Reduction and Refinement) in pre-clinical research (60).

This is a two stage trial in patients with brain metastases and symptomatic cerebral oedema. Although we anticipate the study findings to be relevant to patients with primary brain tumours, and that such patients would be included in a future definitive efficacy study, we have excluded them from the current trial because (a) at initial diagnosis patients with high grade primary brain tumours will most likely need early surgical or other intervention and (b) clinical experience suggests that at relapse the dexamethasone dose they require is much more variable.

Stage 1:

Single arm, pharmacokinetic/dose confirmation

Stage 2:

Randomised, double blind, placebo controlled evaluation of micronised progesterone as a steroid sparing agent. Randomisation will be 1:1, with stratification by clinical site (Leeds and Liverpool).

Randomisation is proposed as there are insufficient historical data on which to base estimates of the “average” reduction in dexamethasone dose in this population over the study period nor of the variability in that dose. Statistical comparison of dexamethasone dosing in the control and micronised progesterone arms is not planned. The control arm will, however, act as a comparator when evaluating dexamethasone dosing in the progesterone arm. While this study is not powered to perform formal statistical analyses, we plan to carry out exploratory work to compare the (i) cumulative dexamethasone dose (ANOVA/t-test or Mann Whitney U if the data are not normal); (ii) final dexamethasone dose (ordered logistic regression) and (iii) time to reach final dose in each arm (Cox regression). The comparator arm will also aid statistical design of the planned, subsequent definitive efficacy trial. Patients in the control arm will receive placebo provided by the manufacturer. This number of patients was chosen empirically, but is similar to the size of a typical “expansion cohort” in Phase 1 oncology trials that seek to better characterise toxicity and inform the design of a future trial; the use of such cohorts appears to increase the likelihood of success in that future trial (60).

2.1. Aims

2.1.1 Primary

- Characterise the pharmacokinetics of oral intermediate dose micronised progesterone in comparison to that achieved by iv dosing in the literature (Stage 1) after a single dose of 200mg and 600mg of micronised progesterone and Stage 2 after repeated (TDS) administration at a dose to be determined. Establish the acceptability, tolerability and safety of a dose of micronised progesterone that achieves the target drug exposure (Stage 2)

2.1.2 Secondary

- Assess the feasibility of structured dexamethasone dose reduction in this population (Stage 2)
- Evaluate patient symptom burden and QoL (Stage 2)

- Make a preliminary assessment of the effectiveness of micronised progesterone by measuring the extent and duration of dexamethasone dose reduction in patients receiving micronised progesterone and a parallel placebo “control” group (Stage 2)

2.1.3 Tertiary

- Describe endocrine, liver function and lipid profiles of patients on micronised progesterone and/or placebo (Stage 2)
- Ensure no undesired CT/MRI changes in tumours (size, enhancement pattern) whilst on micronised progesterone/placebo (Stage 2)
- Establish the acceptability and feasibility of PROMs (Stage 2)
- Evaluate the acceptability of a subsequent randomised controlled trial (Stage 2)

2.2. Endpoints

2.2.1 Stage 1

2.2.1.1 Primary:

Pharmacokinetic profile (including C_{max}, Cl and AUC) of micronised progesterone after single doses of 200mg and 600mg in >4 of 6 patients that allow estimation of serum progesterone exposure (AUC) that is 50 – 150% of that targeted in order to determine the dose in Stage 2..

2.2.2 Stage 2

2.2.2.1 Primary:

- ≥ 13 of 18 patients able to tolerate micronised progesterone until the end of the 14-day treatment period at a dose predicted to achieve the target progesterone exposure.
- Trough progesterone concentrations within 50 – 150% of target

2.2.2.2 Secondary

- Compliance with the structured dexamethasone dose reduction guidelines at 75% of decision points in at least 13 of 18 patients in line with protocol guidelines and as clinically appropriate.
- Description of dexamethasone related symptoms and QOL.
- Percentage of patients achieving a $\geq 50\%$ reduction in dexamethasone dose taken on Day 14
- Comparison (progesterone v placebo) of final dexamethasone dose on Day 14

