3.1.6 Stage 2: Randomised, double-blind, placebo pharmacokinetic/dose confirmation

Please refer to Stage 2: Schedule of activities (Appendix 5).

Please note that patients in Stage 1 are excluded from participating in Stage 2. Both are separate subsets of patients and will have a separate consent form.

We will recruit 36 evaluable patients from Leeds and Liverpool over 18 months (1 patient/month at each site), who will receive oral micronised progesterone/placebo three times a day (t.d.s.) at an initial dose determined in Stage 1; patients who are not evaluable will be replaced. The on-study starting dose of non IMP dexamethasone will be 8mg/day, which will be modified as described in Section 11.

Patients will be treated and blood collected on the NIHR Leeds Clinical Research Facility and Clatterbridge Cancer Centre, Liverpool according to the Schedule of Events. Pharmacokinetic assays and analyses will be undertaken at the University of Bradford.

Please refer to Section 11 for detail on the non IMP dexamethasone and IMP micronised progesterone/placebo dose and administration.

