11.2 Dexamethasone (standard care – non IMP)

Dexamethasone is also prescribed to patients in the PROSSPER trial but is the non IMP and will be supplied from hospital stock.

Dexamethasone will be prescribed as standard of care taken orally in the morning within 30 minutes of finishing breakfast.

At time of randomisation, patients must have been on 4mg-12mg of dexamethasone for at \geq 48 hours.

Stage 1: Day 1 – 10 (Please refer to Appendix No.6 - Doses Stage 1)

Pharmacokinetic sampling days are Day 1 and one other day between Days 5 and 10. This day will be decided by the clinical team and patient

On Day 1, patients will take 8mg dexamethasone in the morning.

On Days 2-10, patients will take dexamethasone in the morning as clinically indicated, except on the second pharmacokinetic sampling day when the dose of dexamethasone will be 8mg.

Stage 2: Day 1 – 22 (Please refer to Appendix No.7 - Doses Stage 2)

On Day 1, patients will take 8mg dexamethasone in the morning.

From Day 3-14, if clinically appropriate, the dexamethasone dose will be reduced by 2mg/day on alternate days (see Appendix 6 [Drug Table Stage 1] and Appendix 7 [Drug Table Stage 2]) and can be discontinued if indicated.

Should symptoms of raised intracranial pressure recur, the dose of dexamethasone will be increased by 4mg (i.e. to 2mg above the dose at which the patient's symptoms had been controlled).

Once the dose has been re-escalated, and after Day 14, subsequent dose adjustments will be at the clinician's discretion.

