15.4 Randomisation and Stratification

After ensuring that the patients meet **all** eligibility criteria and has consented to participate in the study, sites will randomise the patient following the instructions described in the PROSSPER work instructions for sites. Once a patient has been randomised, a patient study number will be issued and this should be used in all correspondence.

Stage 2 of the PROSSPER trial will be randomised into two treatment groups: Progesterone arm or placebo arm. Randomisation will be a 1:1 allocation; 18 patients in each group stratified by clinical site (Leeds and Liverpool).

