15.5 Analysis Plan

The final analysis will be performed on the evaluable population (that is, patients who successfully completed the 14-day treatment period and were not subsequently found to be ineligible); no interim analysis is planned. Unless otherwise stated, 80% confidence intervals will be used; 1-sided p-values calculated and $\alpha=0.05$ as a threshold for significance. Substantial missing data (i.e., missing in >10% patients) will be highlighted in statistical study reports but not imputed. A full statistical analysis plan will be developed prior to any analyses being performed.

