14.4 Final analysis

The final analyses will be performed once the end of study has been declared. They will address each endpoint explicitly with evidence, including:

- Stage 1, primary endpoint (Section 2.2.1.1 Primary:) – to be assessed at end of Stage 1
 - Percentage of target exposure for each patient will be calculated and presented. Subsequent counts of number of patients to achieve 50-150% of target exposure will be presented.
- Stage 2, primary endpoint (Section 2.2.2.1 Primary:) – to be assessed at end of Stage 2
 - Number of patients tolerating progesterone until the end of the 14-day treatment period will be calculated and presented. Note that at least 13/18 patients should

be identified as tolerating progesterone (i.e., ensuring that >50% patients, using 80% CI, tolerate the treatment).

- Stage 2, secondary endpoint (Section 2.2.2.2 Secondary) – to be assessed at end of Stage 2
 - Compliance data will be presented and the number of patients complying with protocol guidelines on dose reduction will be calculated and presented. Note that at least 13/18 patients should be identified as complying with the dose reduction guidelines, to demonstrate compliance (i.e., ensuring that >50% patients, using 80% CI, comply).
 - Dexamethasone related side-effects will be coded according to the CTCAE toxicity criteria. These data will be presented in several ways, including worst value over the trial period for each patient and tabulation of all side-effects graded \geq grade 1 in at least 10% of patients.
 - Presentation/analysis of QoL (DSQ-C, EORTC QLQ-30 & BN20) data.
 - Calculation of percentage reduction in dexamethasone at Day 14.
 - Comparison of final dexamethasone dose in the progesterone and placebo arms (e.g., by ordered logistic regression).
 - Comparison of cumulative dexamethasone dose in the progesterone and placebo arms (e.g. by ANOVA/t-test or Mann Whitney U if normality assumptions are violated).
 - Comparison of time to reach final dose in each arm in the progesterone and placebo arms (e.g., Cox regression).
- Stage 2, tertiary endpoint (Section 2.2.2.3 Tertiary) – to be assessed at end of Stage 2
 - Presentation of relevant lab results to assess endocrine, liver function and lipid profiles in patients on progesterone.
 - Comparison (progesterone v placebo) of CT/MRI data (including tumour size, enhancement pattern etc)

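### The taper-feasibility mark of 13 of 18 does not say which 18 patients count, although all 36 Stage 2 patients follow the same blinded taper; a mark set on all 36 would be more reliable

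*Protocol*

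**What the plan says.** The secondary aim in Protocol section 2.1.2 is stated for the population and not for one arm: "Assess the feasibility of structured dexamethasone dose reduction in this population (Stage 2").

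The endpoint in 2.2.2.2 is "Compliance with the structured dexamethasone dose reduction guidelines at 75% of decision points in at least 13 of 18 patients". The analysis in 14.4 Final analysis repeats that "at least 13/18 patients should be identified as complying with the dose reduction guidelines, to demonstrate compliance" and gives the reason as "ensuring that >50% patients, using 80% CI, comply". Section 15.5 makes this the default standard, "Unless otherwise stated, 80% confidence intervals will be used; 1-sided p-values calculated", and sets 0.05 as the threshold for significance. It also limits the final analysis to evaluable patients, meaning eligible patients who completed the 14-day treatment period.

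On numbers, section 3.1.6 says "We will recruit 36 evaluable patients from Leeds and Liverpool over 18 months", and section 15.4 says "Randomisation will be a 1:1 allocation; 18 patients in each group stratified by clinical site (Leeds and Liverpool").

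On the taper, section 11.2 says "From Day 3-14, if clinically appropriate, the dexamethasone dose will be reduced by 2mg/day on alternate days". Neither that section nor Appendices 5 and 7 distinguish between the arms. Section 3.8 expects the reduction protocol to affect dosing in the control arm as well.

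**The concern.** The question is whether a structured taper can be followed in these patients. Thirty-six patients will supply an answer, all on the same taper, with patients and sites blind to allocation. The pass mark nevertheless has a denominator of 18, and the protocol does not identify those 18. The tolerability endpoint in 2.2.2.1 uses the same 13 of 18. There the denominator explains itself, because only 18 patients take progesterone. For taper compliance it does not.

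Two things are at stake. First, two analysts could apply the criterion to different patients and reach different conclusions. Second, a rule based on 18 is less precise than the trial's own data allow. Section 9.1 lists verification of the dose reduction protocol among the success criteria, and section 3.8 foresees its use in the next trial, so a wrong verdict of not feasible would matter. The protocol itself fixes the numerator, the denominator and the justification, so an analysis plan could not move to 36 without contradicting it.

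**Working it through.** **Inputs.** Mark 13 of 18, and lower 80% limit above 50% (2.2.2.2; 14.4 Final analysis). One-sided 0.05 (15.5). 36 evaluable patients, 18 per arm (3.1.6, 15.4). True compliance rate: not given in the protocol, so 70%, 75%, 80% and 85% are assumed.

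**Step 1: reproduce 13/18.** The exact (Clopper-Pearson) lower limit of a two-sided 80% interval for r successes in n is the 10th percentile of a Beta(r, n − r + 1) distribution.
- 12/18: Beta(12, 7) gives 0.488, below 0.50.
- 13/18: Beta(13, 6) gives 0.545, above 0.50.

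So 13 is the smallest passing count, as the protocol states. The chance of passing when true compliance is only 50% (the false pass) is P(X ≥ 13 | 18, 0.5) = 4.8%. With 12/18 it would be 11.9%. With 18 patients, 13 therefore satisfies both the 80% interval rule and the one-sided 0.05.

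**Step 2: the same method with 36 patients.**
- 22/36: 80% lower limit 0.491, fails.
- 23/36: 80% lower limit 0.519, passes; false pass 6.6%, above 0.05.
- 24/36: 80% lower limit 0.547; false pass 3.3%. The exact 90% lower limit, which matches one-sided 0.05, is 0.517 for 24/36 and 0.488 for 23/36.

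With 36 patients the two standards part: 23 meets the interval rule only, and 24 is the smallest count that meets both.

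**Step 3: risk of a wrong verdict of not feasible.** This is P(X < mark | n, p), exact binomial.

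| True compliance (assumed) | 13/18 | 23/36 | 24/36 | 26/36 |
|---|---|---|---|---|
| 70% | 47% | 16% | 26% | 53% |
| 75% | 28% | 5% | 9% | 27% |
| 80% | 13% | 0.7% | 2% | 9% |
| 85% | 4% | <0.1% | 0.1% | 1.4% |
| False pass at 50% | 4.8% | 6.6% | 3.3% | 0.6% |

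At every rate shown, 24/36 has a lower false-fail risk than 13/18, and its false pass is lower too. Doubling both numbers to 26/36 loses most of the gain, because it keeps the observed proportion at 72% although a larger sample needs a smaller margin above 50%.

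**Step 4: the per-arm reading.** If each arm must reach 13/18, and the arms are independent with equal rates, the chance that at least one fails is 1 − P(X ≥ 13 | 18, p)².
- 70%: 1 − 0.534² = 71%
- 75%: 1 − 0.717² = 49%
- 80%: 1 − 0.867² = 25%

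**The case against.** **The 13/18 mark is not a mistake.** This stands. It follows exactly from the reason given in 14.4 Final analysis, and its false pass meets the one-sided 0.05. The weakness is the choice and naming of the denominator.

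**No data need be lost.** A reader might infer that half the data are thrown away. The text does not support that: 14.4 Final analysis says compliance data will be presented and does not limit this to one arm. Only the pass/fail criterion is affected, and only if it is read as one arm. A per-arm reading uses everyone, although Step 4 shows what it costs.

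**A wrong failure is not shown to be likely.** A reader might infer that the rule will probably reject a workable taper. That depends on a rate the protocol does not give. The risk with 13/18 is about even at 70% and only 4% at 85%. The definition may also be lenient, since 2.2.2.2 allows for what is clinically appropriate: if a justified decision not to reduce counts as compliant, high rates are plausible. This stands.

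**The placebo arm need not be the harder test.** No section says it is. The endpoint is adherence to the guidelines, not success in lowering the dose.

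**Pooling can hide a weak arm.** This stands as a limitation. A total of 24/36 could arise from 18/18 in one arm and 6/18 in the other, so by-arm results must be shown beside it.

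**The trial is a pilot with an empirically chosen size (15.3).** True, but the improvement needs no extra patients.

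**Conclusion.** The point holds in a limited form. The protocol states a pass mark on 18 unnamed patients for an aim that covers a blinded population of 36 on one taper. Under the one-arm reading the criterion is less precise than the data allow; under the per-arm reading it is considerably stricter than it appears. Using all 36 with a mark of 24 cuts the risk of a wrong not-feasible verdict from 47%, 28%, 13% and 4% to 26%, 9%, 2% and 0.1% at 70%, 75%, 80% and 85% true compliance, and lowers the false pass from 4.8% to 3.3%.

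These figures assume independent patients, one common compliance rate in both arms, and the full 36 evaluable patients. The range of rates is an assumption, and the gain in absolute terms is small if true compliance is 85% or higher. The documents do not support a claim that 13/18 is miscalculated, that compliance data are discarded, or that a false failure is the expected outcome.

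**What to change.** In 2.2.2.2 and 14.4 Final analysis:
- Name the denominator as all evaluable Stage 2 patients in both arms. The evaluable definition in 15.5 can stay as it is; whether to count everyone who starts the taper is a separate question.
- Set the mark at 24/36 and give its basis as exact one-sided 0.05 against 50%. The 80% interval rule alone would give 23/36, with a 6.6% false pass. Do not double the mark to 26/36.
- State that the mark is re-derived by the same exact method if the number of evaluable patients is not 36.
- Report compliance by arm, descriptively, next to the pooled result.

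The cost is wording only: Appendix 5 already schedules dexamethasone dose reviews for every Stage 2 patient. The one drawback is that a pooled pass could mask poor compliance in one arm, which the by-arm report is there to show.

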1.3.2 Dose of dexamethasone

The optimal dose of dexamethasone is not known (8). Clinicians generally initiate a high dose of dexamethasone (e.g. 16mg/day) that is reduced as symptoms improve over successive days (8). In some patients, dexamethasone can be stopped, usually following effective local treatment with surgery or radiotherapy, but many patients remain on long-term dexamethasone.

To date, most brain tumour studies have not looked at the effect of treatment interventions on the dose of dexamethasone a patient requires. However, a recent European study of anti-VEGF monoclonal antibody bevacizumab (Avastin™) plus radiotherapy and temozolomide in patients with newly diagnosed glioblastoma did report changes in dexamethasone dose (25). In patients taking dexamethasone, discontinuation (defined as being off dexamethasone for ≥ 5 days) occurred in two thirds of those on bevacizumab compared with less than half of those receiving placebo (66.3 and 47.1%, respectively).

The International Response Assessment in Neuro-Oncology (RANO) Working Group has published standardised endpoints for evaluating corticosteroid use in neuro-oncology clinical trials (5,26). “Responders” are defined as patients with a 50% reduction in total daily dexamethasone dose compared to a baseline dose of ≥4mg/day, or reduction in the total daily dose to ≤2mg. Responders must also have a stable or improved Neurological Assessment in Neuro-Oncology (NANO) score or Eastern Cooperative Oncology Group (ECOG) and an improved score on a relevant clinical outcome assessment tool.

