Appendix 5 – Stage 2: Schedule of activities

Dosing	Day -2 and -1	Day 1	Day 2	Day 3	Day 4	Day 5	Day 6	Day 7	Day 8	Day 9	Day 10	Day 11	Day 12	Day 13	Day 14	Days 15 - 21	Day 22 ⁸
Dexamethasone (mg) – non IMP	8	8	8	6 [#]	6 [#]	4 [#]	4 [#]	2 [#]	2 [#]	0 [#]	0 [#]	0 [#]	0 [#]	0 [#]	0 [#]	As clinically indicated	As clinically indicated
Micronised progesterone/ placebo t.d.s. - IMP		*	*	*	*	*	*	*	*	*	*	*	*	*	*		
Activity	Day -7 to Day -1																
Symptom directed physical examination	X	X							X						X		X
Medical History	X																
Pregnancy ⁵	X																
Neuro. exam ¹		X							X						X		X
Weight/BMI		X							X						X		X
BP, pulse, temp		X							X						X		X
AE review and Dex/IMP dose review	X		X		X		X		X		X		X		X	X ⁷	X
Concomitant Medications Review	X	X							X						X		X
Full blood count	X	X							X						X		X
Clotting profile	X	X							X						X		X
U & E, LFT, Ca	X	X							X						X		X
Hormone profile ²		X													X		

Progesterone/placebo PK blood samples ³		X							X						X		
Side-effects diary		X	X	X	X	X	X	X	X	X	X	X	X	X	X	X	X
Patient Interview ⁴																X	
DSQ-C		X													X		
EORTC QLQ-C30		X													X		
EORTC BN20		X													X		
CT/MRI brain ⁶	X														X		

On Day 3 to day 14, if clinically appropriate, the dexamethasone dose will be reduced by 2mg/day on alternate days and can be discontinued if indicated. See Appendix 7 Drug Table Stage 2 for further detail

* Dose determined in Stage 1 and modified as per protocol

¹ Neurological assessment will also be completed at any time dexamethasone dose needs to be increased

² Patient will be asked to fast (water only) and avoid taking their dexamethasone and progesterone/placebo before the blood sample is taken between 8.00am – 10.00am. After which they should take their prescribed dexamethasone and progesterone/placebo. "Hormone bloods" include: cortisol, glucose, testosterone, lipids; HbA1c, TSH, free T4, FSH, LH, oestrogen, IGF-1.

³ Trough progesterone and dexamethasone levels. Prior to dose of progesterone (or placebo) and dexamethasone. These will be between 8.00am-10.00 am where the patients will already be delaying taking the medication.

⁴ To be completed once between Day 15 and Day 21. Approximately 15 patients will be approached for the patient interview.

⁵ WOCBP – Woman of child bearing potential only

⁶ CT/MRI brain – Within 14 days of screening visit.

⁷ Alternate days.

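### The Day 14 endpoint of a 50% dexamethasone reduction is defined on dose alone, so a patient who has worsened clinically can count as a success; its reference dose is unstated and the exploratory dose comparisons are unadjusted

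*Protocol*

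**What the plan says.** **Endpoint.** Protocol 2.2.2.2 lists as a Stage 2 secondary endpoint the percentage of patients with at least a 50% "reduction in dexamethasone dose taken on Day 14". The matching line in 14.4 reads "Calculation of percentage reduction in dexamethasone at Day 14". Neither line names a reference dose or a clinical condition.

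**Cited definition.** Section 1.3.2 describes the RANO working group's responder: a 50% fall from a baseline of at least 4 mg/day, or a fall to 2 mg or less. It adds "Responders must also have a stable or improved Neurological Assessment in Neuro-Oncology (NANO) score or Eastern Cooperative Oncology Group (ECOG"), together with an improved score on a relevant clinical outcome assessment.

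**Doses.** Section 11.2: "At time of randomisation, patients must have been on 4mg-12mg of dexamethasone for at" least 48 hours. Section 3.1.6: "The on-study starting dose of non IMP dexamethasone will be 8mg/day". In Appendix 5 the row "Dexamethasone (mg) – non IMP" shows 8 mg already on Days -2 and -1. If symptoms of raised intracranial pressure recur, 11.2 says "the dose of dexamethasone will be increased by 4mg"; later adjustments are left to the clinician.

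**Clinical scales.** Section 3.3 includes ECOG and NANO in clinical review. Appendix 5 schedules a neurological examination on Days 1, 8, 14 and 22, and whenever the dexamethasone dose has to be increased.

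**Comparisons.** Section 14.4 gives "Comparison of cumulative dexamethasone dose in the progesterone and placebo arms (e.g. by ANOVA/t-test or Mann Whitney U if normality assumptions are violated") and suggests ordered logistic regression for the final dose. Section 2 names the same methods as exploratory. Randomisation is stratified by site (15.4), but no covariate is mentioned.

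**The concern.** Steroid sparing means needing less dexamethasone while staying clinically stable. Section 9.1 puts it that way itself, speaking of the dose needed to control symptoms. An endpoint that looks only at dose cannot tell a patient who needs less drug from one who is on less drug and doing worse.

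The unstated reference dose adds a second ambiguity. Patients may enter on anything from 4 to 12 mg and are then all placed on 8 mg, so the same Day 14 dose can be a large reduction or none.

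Section 2 says the control arm is there to help design the definitive trial. A success rate whose meaning is open is a weak planning figure for that purpose. Separately, comparing doses without the stratification factor or the pre-trial dose, and letting a normality check choose the test, gives up precision that a trial of 36 patients can ill afford.

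**Working it through.** **1. The plan's own figures.** The protocol gives no expected rate or power for the 50% endpoint. Its power figures in 15.3 concern dose as a continuous outcome. For a one-sided two-sample t-test with alpha 0.05 and 18 per arm (noncentral t, 34 degrees of freedom):

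| Effect size | Protocol | Recomputed |
|---|---|---|
| 1.00 | 90% | 90.2% |
| 0.85 | 80% | 80.3% |
| 0.88 (final dose, simulated) | 83.05% | 82.7% |
| 1.04 (cumulative dose, simulated) | 92.13% | 92.1% |

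These reproduce to within 0.4 percentage points. The sample size does not rest on the 50% endpoint, so nothing below alters it.

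**2. Recurrence under the protocol's own rule.** Dose after recurrence = dose at recurrence + 4 mg (11.2). Reduction = (8 − new dose)/8.

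| Dose at recurrence | Dose after | Reduction from 8 mg | Meets 50%? |
|---|---|---|---|
| 0 mg | 4 mg | 50% | yes |
| 2 mg | 6 mg | 25% | no |
| 4 mg | 8 mg | 0% | no |
| 6 mg | 10 mg | −25% | no |

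Appendix 5 allows 0 mg from Day 9, so recurrence at 0 mg before Day 14 is possible. Such a patient, if still on 4 mg on Day 14, meets the endpoint whatever the neurological findings that day. So does any other patient on 4 mg or less whose NANO or ECOG has worsened without a dose increase.

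**3. Reference dose.** Cross entry doses of 4, 6, 8, 10 and 12 mg with Day 14 doses of 0, 2, 4, 6 and 8 mg, giving 25 cells. Score each by (8 − Day 14 dose)/8 and by (entry − Day 14 dose)/entry. Three cells change class:

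| Entry | Day 14 | Against 8 mg | Against entry dose |
|---|---|---|---|
| 4 mg | 4 mg | 50%, counts | 0%, does not |
| 6 mg | 4 mg | 50%, counts | 33%, does not |
| 12 mg | 6 mg | 25%, does not | 50%, counts |

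The other 22 cells are classified alike. The changes run in both directions, and the protocol gives no distribution of entry doses, so their net effect is unknown.

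**4. Dose before Day 1.** Section 11.2 has patients on 4 to 12 mg at randomisation; Appendix 5 has 8 mg on Days -2 and -1. If randomisation falls on or just before Day 1, the two do not fit. If it falls before Day -2, they can. The protocol does not fix that day.

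**5. Adjustment.** If site and pre-trial dose explained a share R² of the outcome variance, the standard error would shrink by the factor √(1 − R²): √0.8 = 0.894 (11% smaller) at R² = 0.2, and √0.6 = 0.775 (23% smaller) at R² = 0.4. These R² values are an illustration only. Nothing in the protocol supports them, and Section 2 says historical data on the variability of the dose are insufficient.

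**The case against.** The strongest reply is that these are exploratory secondary analyses. Section 2 says no statistical comparison of dosing is planned, 11.8 says there will be no formal efficacy comparison, and 15.3 makes safety primary. The methods in 14.4 are introduced as examples, and 15.5 promises a full analysis plan, where a reference dose or covariate could be settled. The RANO definition stands in the background section and is not adopted by 2.2.2.2. Dose also partly reflects symptoms, because reduction happens only if clinically appropriate and recurrence triggers an increase.

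Much of this stands, and it limits the point to an inexpensive improvement. It does not remove it: what counts as success is an endpoint definition, which the protocol fixes, and the recurrence rule still lets the 0 to 4 mg patient through.

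Stronger readings are tempting but not supported:

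- A reader might infer that patients with an unchanged dose count as successes. That needs 8 mg as the reference, which the protocol does not state, and an entry dose of exactly 4 mg. Against 8 mg, nobody taking more than at entry can count, since success means 4 mg or less and entry is at least 4 mg.
- A reader might infer that the pre-trial dose is the correct baseline. It is a trade-off, because it brings the trial's own reset into the outcome. A 12 mg entrant is credited with (12 − 8)/12 = 33% on Day 1 before any taper, while a 4 mg entrant is moved up to 8 mg and must reach 2 mg.
- A reader might infer that adjustment lifts power from 80% to 87–94%. That takes the assumed R² of 20–40% together with an effect size of 0.85, which 15.3 discusses for the final dose, whereas the t-test criticised here is for cumulative dose.

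**Conclusion.** The point holds as a definitional weakness of an exploratory secondary endpoint. As written, the 50% endpoint can count a patient who is clinically worse on Day 14, and the protocol's own re-escalation rule provides a concrete route: 0 to 4 mg, exactly 50% of 8 mg. That example assumes 8 mg as the reference and that the patient is still on 4 mg on Day 14. How many patients would be affected cannot be derived from the protocol.

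The missing reference dose changes the classification in three of 25 combinations, in both directions. Randomisation should balance entry doses on average, so the harm is mainly to the meaning of the rate and its use in planning the next trial, rather than bias between arms. Adjusting for site and pre-trial dose is sound practice here, but its gain in precision cannot be quantified from the protocol. The primary endpoints and the sample size are untouched.

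**What to change.** In 2.2.2.2 and 14.4:

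1. Count a patient as a success only if the dose criterion is met and NANO or ECOG on Day 14 is stable or improved from Day 1. State how the two scales combine if they disagree. Report the dose-only rate alongside. This takes over the neurological part of the definition in 1.3.2, not the whole of it.
2. State the reference dose. Report the percentage reduction both against the Day 1 dose of 8 mg and against the dose taken before the trial imposed 8 mg. The latter wording matters, because under Appendix 5 the last 48 hours before Day 1 may already be at 8 mg.
3. Reconcile 11.2 with the Day -2 and -1 entry in Appendix 5.
4. In 14.4 and Section 2, replace the normality-dependent choice between t-test and Mann-Whitney for cumulative dose with ANCOVA. Keep ordered logistic regression for final dose. Adjust both for site and pre-trial dose.

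The cost is a few lines of text and slightly more analysis. The scales are already part of clinical review and a neurological examination is already scheduled on Days 1 and 14, so no visit is added. The clinical condition can only leave the rate equal or lower it; the effect of a different reference dose could go either way.
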